3 STUDY DESIGN

We will pursue a two-arm CRCT with a total of 50 clusters of 5x5 city blocks each, including at least 92 enrolled age-eligible participants per cluster, with 25 clusters randomly allocated to receive TIRS and 25 clusters not receiving TIRS (Fig 5) (see section 4.4 in the Clinical Trial Protocol). A total of 4,600 age-eligible individuals will be recruited for the trial. This sample size accounts for a 20% loss to follow-up. Routine MOH vector control actions (primarily, truck-mounted ULV spraying of chlorpyrifos, larvicide with altosid® and indoor space spraying in premises of suspected ABV cases) performed in response to symptomatic ABV cases reported to the healthcare system will not be interrupted and could occur across both study arms. Therefore, our trial will compare TIRS to routine ABV prevention and control, providing an opportunity to quantify intervention efficacy and potential benefits in comparison to existing practice. Clusters will be located within the areas identified as hot-spots of ABV transmission[40] (Fig. 5). Placing all clusters within the zone of high ABV incidence will increase power by focusing on an area with higher event rates and lead to a more homogeneous design (e.g., less likely to have imbalance across trial arms). We will use a covariate-constrained randomization strategy[41] to randomly select 50 clusters from the set of census tracts in the hot-spot region. This approach ensures that key cluster-level variables (e.g., historical ABV transmission, population size and density, % employed population) are not more than 10% different between trial arms and maximizes the distance between neighboring clusters. To further reduce contamination and edge effects, while all households in TIRS clusters will be offered the intervention, epidemiological and entomological evaluation will occur in the center of each cluster, following a “fried egg” design (blue blocks in inset of Fig. 5). Enrollment into the trial will occur in all clusters before TIRS allocation has been determined, in order to prevent selection bias.

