6.2 Sample Size Considerations

The size of clusters for the intervention will be 5x5 city blocks. This extent was chosen because: a) the area is large enough to contain more than the 92 age-eligible children required for the epidemiological evaluation; b) *Ae. aegypti* dispersal is limited, rarely exceeding 100m[58], thus concentrating our evaluation in the center of the cluster will provide a less biased estimate of intervention efficacy; c) prospective mobility surveys informing how human mobility may affect the placement of clusters. Surveys performed on 800 FSD residents showed that FSD cohort participants living in Merida had about 60% their mobility occurring within 1km of the house (Fig 7).

Given the large extent of movement, separating clusters by distance (e.g., larger than 1 km separation) would be unfeasible. Instead, our approach for the trial was to focus on a “fried egg” design, where entomology and epidemiological follow-up of study participants will occur within the central 3x3 city blocks of the 5x5 city-block cluster (Fig 8).

Randomization:

The study area includes 286 hot-spot census tracts, 192 of which have total population size of at least 1,000, per the 2010 census. Census tracts are categorized into four sectors. For each census tract, we have characterized the following features that are used as balancing factors:

- Population size, per 2010 census.
- Population density, per 2010 census.
- Percent employed population, per 2010 census.
- Cumulative number of ABD cases between 2008 and 2016 (per passive surveillance).

[figure not shown]

Fig. 7. Probability of moving a given distance from the home (y-axis) as a function of the distance from home (x-axis) for Merida residents, and stratified by age group ([name] et al. unpublished).

Fig. 8. Structure of a study cluster. Yellow areas will receive TIRS, whereas blue areas will receive TIRS and participate in the epidemiological and entomological evaluation of the intervention.

We simulated 1,000,000+ random allocation patterns (25 clusters in group A, 25 clusters in group B – allocation to TIRS/routine vector control determined later), and we use covariate-constrained randomization[41] to eliminate the allocation patterns with an imbalance of $\pm 10\%$ on any of the continuous balancing factors listed above. Specifically, for each balancing factor, if for a given allocation pattern, the mean of group A divided by the mean of group B was greater

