than 1.1 or less than 1/1.1, that pattern would not be considered for potential selection. Furthermore, we eliminate any allocation pattern with imbalance in the number of clusters per arm per sector greater than ± 1 . We will implement checks to satisfy the criteria that the design is not overly constrained, as proposed by Moulton[41] (e.g. pairs of clusters always or never appearing in the same arm). For each retained allocation patterns, we calculate the mean distance from the centroid of each cluster to the centroid of its nearest neighbor also in the trial. We restrict to the top 10% of allocation patterns with the largest mean distance. Preliminary exercises returned over 1,500 allocation patterns satisfying all selection criteria. Sample allocation patterns are plotted in Fig 9.

Given the set of allocation patterns that meet the above balancing criteria, we will use equal probability sampling to randomly select one allocation. For participant enrollment, the study teams will be provided with a list of 50 census tracts for inclusion in the study, without record of which census tracts are in Group A or B. At this time, households and individuals will be invited to participate in the study. No participant or investigator will have knowledge of their allocation. **After completing the enrollment process, we will then use a random number generator to determine which group (A or B) is allocated to TIRS, where each group has a 50% probability.**

Power and sample size

To assess power and sample size requirements, we analyzed historical passive surveillance data from the 192 hot-spot census tracts with population size of at least 1,000 (from our publication characterizing the ABV hot-spot area [40]). We use yearly data from 2008 to 2016 on the number of dengue, chikungunya, and Zika cases recorded in children 0-14 years each year by census tract[40]. Data were combined into pairs of adjacent years to mimic a two-year trial period. The table below summarizes the mean incidence (number of cases over two-year period/number of children) and intracluster correlation coefficient (ICC) for a given two-year period.

Data source	Mean	ICC
2008+2009 Dengue	0.0402	0.0345
2009+2010 Dengue	0.0530	0.0289
2010+2011 Dengue	0.0572	0.0164
2011+2012 Dengue	0.0847	0.0153
2012+2013 Dengue	0.0729	0.0188

[figure not shown]

Fig 9. Two examples of outputs from the constrained randomization into two groups.

2013+2014 Dengue	0.0455	0.0256
2014+2015 Dengue/Chik	0.0581	0.0229

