2015+2016 Any	0.0385	0.0151

For our sample size calculations, we conservatively assume a low incidence (4% over a two-year period) and high ICC (0.035). Sample size is shown below for 50 clusters, considering 80% power and 90% power and TIRS efficacy from 70 to 90%. Sample sizes are adjusted for the study design effect and expected 20% loss to follow-up (LTFU).

POWER	TIRS EFFICACY	NUMBER OF EVENTS	TOTAL EFFECTIVE SAMPLE SIZE	NUMBER PER CLUSTER, UNADJUSTED	NUMBER PER CLUSTER, ADJUSTED FOR LTFU	TOTAL SAMPLE SIZE, ADJUSTED FOR LTFU
90%	70%	38	1390	>500		
	75%	30	1164	122	152	7600
	80%	24	984	62	77	3850
	90%	16	714	28	35	1750
80%	70%	28	1038	74	92	4600
	75%	22	870	43	54	2700
	80%	18	734	30	37	1850
	90%	12	534	17	21	1050

Assuming 4% incidence over a two-year period, 70% TIRS efficacy, an ICC of 0.035, and 20% loss to follow-up, we will require 92 age-eligible children enrolled per cluster for an overall sample size of 50 clusters and 4,600 children to have 80% power to detect a significant reduction in ABV incidence with TIRS.

Figure 10 below summarizes the distribution of the number of children less than or equal to 14 years of age in each cluster, based on the 2010 census. The minimum size is 145 children. The median is 546 children.

[figure not shown]

Figure 10. Distribution of children aged 0-14 per cluster, based on 2010 census.

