Consent will be obtained in participants' homes. Study personnel will visit all houses in the 5x5 city block clusters in a door to door fashion (when seeking household consent) or visit houses located in the center 3x3 city blocks of the 5x5 block cluster (when seeking individual consent). Study explanations are usually provided to small groups of adults present in the household, whereas written consent or assent are obtained from each individual participant.

Subjects may voluntarily withdraw their consent for study participation at any time without penalty or loss of benefits to which they are otherwise entitled. If a subject withdraws or is withdrawn prior to completion of the study, the reason for this decision will be recorded in a case report form (CRF). The reasons, might include, but are not limited to:

- Subject no longer meets eligibility criteria
- Subject becomes noncompliant
- Medical disease or condition, or new clinical finding(s) for which continued participation, in the opinion of the investigator might compromise the safety of the subject, interfere with the subject's successful completion of this study, or interfere with the evaluation of responses.
- Subject lost to follow-up

8.1 Informed Consent/Assent Process (in Case of a Minor or Others Unable to Consent for Themselves)

Assent to participate and a parentally signed informed consent document will be obtained for 11-15 year olds. The consent document follows Emory IRB policy for working with minors, and includes a section separating those individuals assenting from those consenting. A copy of the form is attached to this application.

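### Can the central 3x3 blocks of every cluster supply the 92 children that the sample size calls for?

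*Combined protocol and SAP*

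**What the plan says.** Section 3 (Study Design) sets the target as 50 clusters of 5x5 city blocks, "including at least 92 enrolled age-eligible participants per cluster", and separately gives a total of 4,600. Section 6.2 derives the figure: "we will require 92 age-eligible children enrolled per cluster for an overall sample size of 50 clusters and 4,600 children".

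Two statements in Section 6.2 bear on whether clusters can supply that number. The reasons for the 5x5 size include that "the area is large enough to contain more than the 92 age-eligible children required for the epidemiological evaluation". The text on Figure 10 then gives the 2010 census count of children up to 14 years per cluster: "The minimum size is 145 children", with a median of 546.

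The same section says that "entomology and epidemiological follow-up of study participants will occur within the central 3x3 city blocks of the 5x5 city-block cluster". Section 8 sends staff to those same central blocks when they seek individual consent. The outer blocks are sprayed in the intervention arm but contribute no participants.

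**The concern.** The supply evidence describes 25 blocks, while recruitment draws on nine. The age bands differ slightly as well: 0-14 in the census count, 2-15 for eligibility. A reader who scales the smallest cluster by 9/25 gets a number well under 92, even if every family agrees.

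The requirement is worded as a minimum for each cluster, and 50 x 92 = 4,600 leaves no slack. The visible selection criteria set no minimum number of children in the core. The block-replacement rule in Section 8 responds to consent below 60%, not to too few children. If many cores fell short and nothing made up the loss, the trial would have fewer children and less power than stated.

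**Working it through.** **Reproducing the 92.** Inputs from Section 6.2: 4% control incidence over two years, 70% efficacy (so 1.2% with spraying), ICC 0.035, 20% loss, 50 clusters, total effective sample size 1,038. Solving 50m / (1 + (m - 1) x 0.035) = 1,038 gives m = 73.3, printed as 74. Then 73.3 / 0.8 = 91.6, so 92, and 92 x 50 = 4,600. The requirement itself is sound.

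**Children in the core**, assuming even density and that the count refers to the 5x5 area:

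- Core share: 9/25 = 0.36.
- Smallest cluster: 145 x 0.36 = 52. With 14 rather than 15 single years of age: 52.2 x 14/15 = 49.
- Median cluster: 546 x 0.36 = 197.
- Whole-cluster count needed for 92 at full participation: 92 / 0.36 = 256.
- At 75% participation (illustrative): 39 in the smallest, 147 in the median, and 92 / (0.36 x 0.75) = 341 needed.
- At 60% participation: 31 in the smallest and 118 in the median.

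So the smallest cluster falls short and the median cluster does not, even at 60%.

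**Power with unequal clusters.** With N the number followed (80% of those enrolled), m the mean followed per cluster and CV the coefficient of variation of cluster size:

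N_eff = N / (1 + ((1 + CV²) x m - 1) x 0.035)

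Power = Φ(0.028 / sqrt(2 x [0.04 x 0.96 + 0.012 x 0.988] / N_eff) - 1.96)

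For equal clusters: 3,680 / 3.541 = 1,039, and power is 0.8125. The numbers of short clusters below are assumed. Graded means evenly spaced from the lowest value up to just under 92.

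| Short clusters | Total enrolled | Power |
|---|---|---|
| None | 4,600 | 0.8125 |
| 1 at 52, others 92.8 | 4,600 | 0.8114 |
| 5 graded from 52, others 94.7 | 4,600 | 0.8100 |
| 10 graded from 52, others 97.5 | 4,600 | 0.8077 |
| 10 graded from 39, others 99.3 | 4,600 | 0.8040 |
| 10 graded from 52, no top-up | 4,380 | 0.8035 |
| 10 all at 52, others 102.0 | 4,600 | 0.7994 |
| 10 graded from 39, no top-up | 4,308 | 0.7987 |
| 10 all at 52, no top-up | 4,200 | 0.7926 |

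With the total held, a short cluster costs little, because at this ICC extra children in one cluster nearly replace those missing from another.

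**Is 36% the right share?** Figure 10 is not shown. Its text speaks of clusters, but the randomization text works with tracts: "the study teams will be provided with a list of 50 census tracts for inclusion in the study", chosen from hot-spot tracts, "192 of which have total population size of at least 1,000, per the 2010 census". If 145 is a tract count, 9/25 does not apply to it. Sections 3.2.8 and 3 put 10% of central houses at about 1,350, so there are about 13,500 core houses, or 270 per core. Section 1.3.1 reports 630 people in 160 houses, 3.9 per house. If that holds here, an average core has about 270 x 3.9 = 1,053 residents, roughly a whole tract at the 1,000 threshold. The core share of such a tract could be far above 36%. In a tract larger than its 5x5 area, it could be lower. At the average, 92 children means 92/270, or about one enrolled child per three core houses.

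**The case for a change.** The best case for a change is that a per-cluster minimum ought to be supported by a per-cluster count from the area that recruits, and averages cannot do that. For the smallest cluster to supply 92, 63% of its children (92/145) would have to live in 36% of its blocks. Full participation is a ceiling, since Section 4.2 also requires a consenting household and excludes visitors and families planning to move. Without a rule for a short core, field staff might recruit from the outer blocks and weaken the protection against edge effects. A tabulation would be cheap.

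Part of this stands: the core count is absent, and taken literally the minimum may be missed in a few clusters. The practical risks are largely covered by the text. Sections 6.2 and 8 already confine consent and follow-up to the core. A minimum of 92 does not stop larger cores from enrolling more, and the 4,600 total tells staff what to aim for. The Section 3 timeline provides for checking that clusters are eligible before enrolment starts. Its example is safety, but a count of core children belongs naturally to that step.

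Harsher scenarios do lower power. Fifteen clusters all at 31 with no top-up would give roughly 0.75 to 0.77. Nothing in the documents suggests that. The value 145 is the minimum, so it cannot be presumed for many clusters at once, and the median is nearly four times as large. If it is the minimum over the 192 candidates, a simple random draw of 50 would include that tract about 26% of the time (50/192); the constrained draw may differ.

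**Conclusion.** No change to the plan is needed. The whole-cluster count does not establish that each core can supply 92 children, and a few small clusters may fall below it. Followed sensibly, with 92 treated as the average that 4,600/50 implies and larger cores making up the difference, the design keeps about the power it claims. The loss is about one percentage point or less with up to ten graded short clusters and the total maintained, and power falls just under 80% only in the severe cases tabulated.

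No bias follows. Children are enrolled before it is decided which group is sprayed, so a short core cannot depend on the arm. The primary Cox model uses individual data and allows for correlation within households and clusters, so unequal cluster sizes need no new method. The planning ICC of 0.035 also exceeds every two-year value tabulated in Section 6.2 (maximum 0.0345).

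This rests on assumed numbers of short clusters, since Figure 10 cannot be read, and on even density for the values 52 and 197. The conclusion would weaken only if a large share of the selected cores were close to the minimum and the missing children were not replaced elsewhere.

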6.3 Participant Enrollment and Follow-Up

The duration of individual participation in the trial will vary, but will not be longer than 4.5 years. Enrollment will occur at the end of Year 1 of the project, and will involve a baseline serological characterization of the population. Since then, and for the following 2-3 years, participants will be involved in the epidemiological assessment of TIRS (which will rely on active surveillance and annual blood draws). On the first two quarters of the 4th year post-enrollment, participants will provide the last annual blood sample to assess their serological evidence of interval infection. We will emphasize participants the fact that we would like people to participate as long as possible within this timeline. Febrile participants are followed clinically during the duration of their illness -- which rarely exceeds 7 days-- and we solicit convalescent samples 14-30 days after an acute sample. Movement and loss to follow-up interviews will last a maximum of 1 hour.

	2020 (Y1)				2021 (Y2)				2022 (Y3)				2023 (Y4)				2024 (Y5)			
Activity by Quarter	Q1	Q2	Q3	Q4	Q1	Q2	Q3	Q4												
Participant Enrollment																				
Baseline Serology and Entomology																				
Active Surveillance																	possible 3 season			
Annual sero-survey																				

Planned secondary analyses of clinical and human serological data include:

- Cox proportional hazards model with time to first laboratory-confirmed symptomatic ABV disease as the endpoint, adjusting for additional cluster- and household-level covariates (e.g. population density, household size, socio-economic status).
- Cox proportional hazards model with time to first laboratory-confirmed symptomatic ABV disease as the endpoint, adjusting for routine human movement as measured by the prospective movement survey (measured in all enrolled participants). The proportion of time in treated areas will be included as a further covariate.
- Disease-specific versions of the primary analysis (e.g. time to first laboratory-confirmed symptomatic dengue disease as the endpoint), if data permit.
- Analysis of recent human movements measured by RMS in enrolled participants presenting with symptoms for laboratory confirmation. The data will be analyzed using a test negative design-type structure, where individuals testing negative for any ABV will

serve as a comparator group for individuals testing positive for ABV. The analysis will adopt recently developed methods for cluster randomized vector control trials ⁸¹.

- Binomial generalized linear mixed effects model to assess the efficacy of TIRS for reducing laboratory-confirmed DENV, CHIKV, or ZIKV infection, analyzed as cumulative incidence over the two (or potentially three) transmission seasons, as measured from annual serological samples.

Entomological endpoints:

Planned secondary analyses of mosquito data include:

- *Ae. aegypti* indoor entomological indices (adult presence and abundance, female presence and abundance, blood fed female presence and abundance) and ABV minimum infection rates (# infected mosquitoes/total mosquitoes tested x 1,000).
- Negative binomial GLMMs will test for differences in treatment and control arms for all entomologic indices as in our previous work, including *Ae. aegypti* infection rates with DENV, CHIKV, or ZIKV, and *Ae. aegypti* indoor entomological indices (adult presence and abundance, female presence and abundance, blood fed female presence and abundance) [34].
- The following *Ae. aegypti* adult indices will be calculated for each sampling date and compared between treatments and over time: presence (binomial variable) and abundance (count variable) of adults, females and bloodfed females per house. Generalized linear mixed effects models (GLMM) nested at the cluster (level 1) and city-block (level 2) levels will be used to compare each entomological index between treatment and control arms. Link functions for GLMMs will be binomial for presence indices and negative Poisson for abundance indices. The best fit models (after comparing AIC values for models including all levels or only Level 1) will be used to calculate odds ratios (OR, for mosquito presence/absence) and incidence rate ratios (IRR, for mosquito abundance) using control houses as the unit of comparison. We will calculate the operational efficacy of the intervention as $E=(1-IRR) \times 100$. This measure, ranging between 0 and 1, describes the percent reduction of mosquito abundance in treated houses with respect to the control. All models will be run with the software package lme4 within the software platform R (<https://www.r-project.org/>).

Transmission modeling

Our existing mathematical model for Yucatan[35, 59] will be used to simulate the effectiveness of TIRS for different scenarios of intervention coverage and insecticide residual power, using the observed trial data as a critical model input. This agent-based model of individual people and mosquitoes incorporates household demography, a spatially heterogeneous population structure based on census and remote sensing data, movement of workers and students, and seasonal fluctuations in mosquito population and incubation period.

We will model TIRS in treated households as (1) reducing the location's susceptible mosquito population and (2) increasing daily mortality probability for infected mosquitoes. For computational efficiency, we represent susceptible mosquitoes probabilistically and infected mosquitoes explicitly. For (1) we use the TIRS efficacy to reduce the susceptible population, and for (2) we calculate a daily additional mortality probability associated with the overall population reduction (e.g. roughly 0.13 for 80% efficacy TIRS). This additional mortality is treated separately from the normal daily mortality due to age or other factors. To calculate daily mortality, we use the assumed TIRS efficacy combined with our empirically-derived model for

mosquito age distribution. The age distribution determines baseline daily mortalities, to which we add a constant daily death probability.

We will use our model to evaluate the effectiveness of TIRS for different scenarios of intervention coverage and insecticide residual power. Different movement (e.g. mosquito vs. human) and transmission (e.g. pathogen introduction and elimination) dynamics become relevant at different spatial scales [16], thus we will predict the impact of scaling-up TIRS to the entire state rather than treating single cities. Simulating epidemiological trends of scaled-up TIRS for periods longer than the duration of our trial (e.g. a decade) will evaluate the effect of changing population-level immunity [35] and generate measures of effectiveness that are more informative for programmatic decision making.

Integrating ABV transmission modeling with the field study will facilitate both interpreting trial results [60] and increasing realism of the model. The explicit spatial structure of our model will allow us to separately calculate direct effects (due a person to living in a treated household) and indirect effects (due to adjacency to treated households) of TIRS as a function of residence position within, or distance from, a treated cluster. We will also use our model to evaluate competing hypotheses for unexpected field results that we observe.

Spatial spread of ABV is driven by both humans and mosquitoes, but because *Aedes* bites during the day when humans are most likely to be away from home, human movement patterns are likely particularly important in driving spatial transmission¹⁶. Our model already represents both human and mosquito movement, but the trial will produce data that will be highly valuable in evaluating and refining both. Survey data about human movements may be used directly by the model, while a probabilistic mosquito movement kernel may be inferred based on spatial autocorrelation patterns in ABV case data collected in the trial.

